Our current understanding of outcomes after treatment with intranasal capsaicin is incomplete. Most studies analyzing the effect of intranasal capsaicin have evaluated a heterogeneous group of non-allergic rhinitis patients with idiopathic rhinitis without distinguishing among subtypes. Consequently, we do not know whether certain subtypes of idiopathic rhinitis are more likely to respond to treatment with intranasal capsaicin treatment than other subtypes. Due to the relative paucity of information regarding therapeutic efficacy of intranasal capsaicin for non-allergic rhinitis, the most recent Cochrane review describes capsaicin as an option for patients with idiopathic, non-allergic rhinitis.⁹ We hope to further delineate the group of idiopathic non-allergic rhinitis patients that will benefit from intranasal capsaicin in an effort to refine the treatment algorithm for non-allergic rhinitis.

Objectives

- Primary: To determine the therapeutic response of non-allergic rhinitis patients that have been subtyped as non-allergic rhinitis with local IgE elevation or non-allergic rhinopathy to intranasal capsaicin based on visual analog scale and optical rhinometry
 - The total as well as individual symptom VAS scores at enrollment, 4 weeks post-treatment, and 12 weeks post-treatment will be compared
 - The maximum optical density determined via optical rhinometry at enrollment and 12 weeks post-treatment will be compared
- Secondary: To determine the prevalence of non-allergic rhinitis with local IgE elevation in this study's cohort of patients with non-allergic rhinitis identified by rhinitis history and negative skin

testing for allergic rhinitis, and to determine the change, if any, in intranasal IgE levels after capsaicin treatment.

- The local IgE level obtained from the brush biopsy of the inferior turbinates at enrollment and at 12 weeks post-treatment will be compared

Study Design

- Prospective cohort study
- The study is expected to last 1 year with subject participation lasting 15 weeks.
- Therapeutic response to intranasal capsaicin will be measured using major nasal symptoms on a visual analog scale, as well as optical rhinometry.

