 - Nasal symptoms of rhinorrhea, nasal obstruction, nasal itching, and sneezing, will be measured using a visual analog score. Results range from 0-10. The major nasal symptom will be defined as the nasal symptom with the highest score on VAS at screening. The pre- and post-treatment data can be compared to measure change in symptoms.
 - Optical rhinometry: Maximum optical density will be recorded following the initial capsaicin challenge, as well as at 12 weeks post-treatment
- Assessment of efficacy will be based on repeat symptoms scores (nasal symptom inventory pre-treatment and at 4 and 12 weeks, optical rhinometry pre-treatment and 12 weeks post-treatment). Additionally, brush biopsy of the inferior turbinates will be performed pre-treatment and 12 weeks post-treatment in order to determine any change in local IgE levels.
- This study is using previously described methods with good safety profiles. Patients may experience minimal pain and some discomfort with the skin prick test for allergy testing, the mucosal swab for IgE levels, and the intranasal capsaicin.
- Patients will receive skin allergy testing with results and clinic visits with physician at no charge. In addition, study drugs will be provided at no cost to the patient. Although no monetary compensation will be provided for participating in the study, study participants will be reimbursed the fee for parking at all three visits.

Study Population

All patients that present with chronic rhinitis not otherwise classified as allergic based on prior positive skin or blood test to the Texas Sinus Institute will be screened for study inclusion.

Inclusion Criteria:

1. Adult > 18 years of age
2. Chronic rhinitis

Exclusion Criteria:

1. Active smoker
2. Anatomic source of nasal symptoms
3. Chronic rhinosinusitis or other nasal infection
4. History of sinonasal malignancy
5. Pregnancy or lactation
6. Use of medication affecting nasal function (topical steroids, topical anticholinergics, oral antihistamines) in the previous 4 weeks
7. Use or abuse of nasal decongestants.
8. Positive skin prick test for allergic rhinitis

Study Procedures

At the first visit after enrollment:

- Rate major nasal symptoms (rhinorrhea, nasal obstruction, nasal itching, and sneezing) on a visual analog scale
- Complete skin prick allergy testing
- A nasal brushing to determine local IgE levels
- Optical rhinometry with intranasal capsaicin challenge to confirm diagnosis of non-allergic irritant rhinitis¹

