 - A cytology brush will be used to brush the inferior turbinates (3 spins of the brush against the medial aspect of the inferior turbinates). The brush is then washed in saline and stored at -20C.
 - Antigen specific IgE will be determined using reference lab from the processed sample.

Intranasal capsaicin treatment

- The intranasal capsaicin treatment will be completed according to the protocol for treatment of non-allergic irritant rhinitis with intranasal capsaicin established by Van Gerven et al.³
 - Patients will be treated with 5 intranasal doses of capsaicin separated by 1 hour
 - Capsaicin solution (Sigma Chemical, St. Louis, MO USA) will be diluted in 1% ethanol and 0.9% normal saline. A mucosal atomizer device (MAdomizer, Wolfe Tory Medical, Inc, Salt Lake City, UT USA) delivering 100 µL solution will be used to deliver a total dose of 2 µg of capsaicin to each nasal cavity for each application. Each application of capsaicin will be preceded by application of 100 µL of aerosolized 1% lidocaine for anesthesia 15 minutes prior to each planned intranasal capsaicin application.

Data and Safety Monitoring

- Serious adverse events are not anticipated. Patients may experience minimal pain and some discomfort with the skin prick for allergy testing, the mucosal brushing for IgE levels, and the intranasal capsaicin.
- The principal investigator will be notified of any adverse events, protocol deviations, and other problems. These will be addressed immediately by the PI or co-investigators.
- On the first of each month, the PI will review the study to ensure that any events or deviations were reported, to ensure that the study is proceeding strictly according to protocol. The status of the study will be reviewed during a monthly meeting with the rhinologic team which consists of Drs. [name], [name] and [name].

Statistics

In considering our sample size calculation, we considered our primary outcome as the change in VAS for the major nasal symptom. Using the study by Gerven et al. to guide a sample size calculation, we assumed a success rate of capsaicin to be 75% with success defined as a decrease of at least 30% on the VAS for the major nasal symptom. In their study, they enrolled 33 patients with non-allergic rhinitis and showed a significant response to intranasal capsaicin treatment via VAS. Consequently, we will plan for 33 patients with non-allergic rhinitis to complete this study.

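### The named primary outcome has no visit and no designated comparison, the primary objective leaves at least 11 comparisons unranked at 0.050, and 33 is set by precedent

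*Combined protocol and SAP*

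**What the plan says.** All references are to the combined protocol and SAP.

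- **Statistics, first paragraph.** For sample size, "we considered our primary outcome as the change in VAS for the major nasal symptom". No visit is attached. The paragraph continues: "we assumed a success rate of capsaicin to be 75% with success defined as a decrease of at least 30% on the VAS". It then notes of the cited capsaicin study that "they enrolled 33 patients with non-allergic rhinitis and showed a significant response to intranasal capsaicin treatment via VAS", and concludes: "Consequently, we will plan for 33 patients with non-allergic rhinitis to complete this study".
- **Objectives, Primary.** The aim is therapeutic response in patients subtyped by local IgE. Two items follow: "The total as well as individual symptom VAS scores at enrollment, 4 weeks post-treatment, and 12 weeks post-treatment will be compared" and "The maximum optical density determined via optical rhinometry at enrollment and 12 weeks post-treatment will be compared".
- **Study Design.** There are four symptoms. "The major nasal symptom will be defined as the nasal symptom with the highest score on VAS at screening". Efficacy rests on both week 4 and week 12 symptom scores.
- **Statistics, second paragraph.** Outcome scores in general are compared by local IgE status (Mann-Whitney U or chi-square) and over time (Wilcoxon signed rank). Neither comparison is assigned to the primary outcome. A 0.050 level applies throughout.
- **Background Information.** The stated gap in knowledge is that "we do not know whether certain subtypes of idiopathic rhinitis are more likely to respond to treatment with intranasal capsaicin treatment than other subtypes".

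**The concern.** A primary analysis needs an outcome, a visit and a comparison. The plan supplies only the first. An analyst could follow it faithfully and still choose, after seeing the data, between two visits and two kinds of comparison. The primary objective adds further scores that also carry the word primary, with no ranking among them.

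The sample size paragraph does not settle the matter. It moves between a change score and a 30% responder definition, and the 75% enters no calculation. Nothing says how precisely 33 patients can answer the subtype question, which the Objectives and Background put at the centre of the study.

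At stake is whether a p-value below 0.050 can be read at face value, and whether a non-significant subtype result would be mistaken for equal response.

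**Working it through.** **1. Can 33 be reproduced?** Not from the stated inputs: 75% success is given without a reference rate or power. With an assumed reference rate of 50%, two-sided 0.05 and 85% power, the normal approximation gives ((1.96 x 0.500 + 1.036 x 0.433) / 0.25)^2 = 32.7, so 33 (exact binomial: 35). One-sided 0.05 with 90% power gives 33 by the exact method. Both need inputs that the plan does not state. The plan's own reason is the earlier study's enrolment.

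**2. Count.** (1 total + 4 symptoms) x 2 post-treatment visits + 1 optical density = 11. The count is derived from the Objectives, not stated there. It excludes the major-symptom score, which is a separate variable because the symptom differs between patients; adding it at both visits gives 13.

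**3. False positives within the named outcome.** 2 visits x 2 comparisons = 4 analyses.
- If independent: 1 - 0.95^4 = 18.5%.
- Simulated change scores with no effect, 33 patients split 16/17 (assumed), between-visit correlation 0.5 to 0.7: about 17% for any of the four, and about 9% for the two visits of one comparison.

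These figures treat the baseline as free of selection; step 5 shows what happens if it is not.

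**4. False positives across the 11 over-time tests.** If independent: 1 - 0.95^11 = 43%. Simulated exact signed-rank tests (n = 33, normal changes, no effect, total = sum of the four symptoms, optical density independent of VAS):

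| Between-symptom r | Between-visit r 0.5 | Between-visit r 0.7 |
|---|---|---|
| 0.2 | 37% | 33% |
| 0.5 | 31% | 29% |
| 0.7 | 27% | 26% |

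The documents give no correlations, so the range is an assumption.

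**5. Selection of the major symptom.** It is the highest of four at screening. If that same score is also the baseline, a later fall is expected with no treatment effect: 0.01 to 0.46 SD over the assumed correlations, with one symptom 0 to 2 SD above the others. The signed-rank test against zero, n = 33, then rejects in about 75% of trials at r 0.2/0.5 (between symptoms/between visits), about 53% at 0.5/0.5 and about 21% at 0.7/0.7 with equal symptom means. This falls to about 5% where one symptom clearly dominates. If baseline is a separate measurement, the artefact is about zero. Study Design says screening, while the Objectives say enrollment; the text does not say whether these are one score or two.

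**6. What 33 can deliver.**
- Whole-cohort mean change: 95% half-width t(32)/sqrt(33) = 2.037/5.745 = 0.355 SD. Signed-rank power is 81% for a change of 0.52 SD.
- Success: 0.75 x 33 is about 25; the exact 95% CI for 25/33 is 57.7% to 88.9%.
- Subtype difference in mean change, half-width t(31) x sqrt(1/n1 + 1/n2): 2.040 x 0.348 = 0.71 SD at 16/17, and 2.040 x 0.486 = 0.99 SD at 5/28.
- Mann-Whitney power for an assumed 0.5 SD difference: 27% at 16/17, 15% at 5/28.

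The 5/28 split is an extrapolation from the only prevalence figure in the documents, 20 of 20 with antigen-specific IgE (Background Information). Its exact 95% lower limit is 0.025^(1/20) = 0.832, which leaves at most 33 x 0.168 = 5.6 expected without elevation.

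**The case against.** The strongest reply is that the plan does name one primary outcome. A reader might infer that any significant result among the 11 could be presented as the primary finding. The documents do not support that: total VAS or optical density could not be called the primary outcome without departing from the Statistics section. The choice left open inside the named outcome is two visits by two comparisons, about 17% rather than 26-37%. This stands, so the larger range describes the unranked primary objective only. Nor do the two sections contradict each other. Each patient's major symptom is one of the four listed, and what is missing is ranking.

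A reader might also infer that 33 is too few. For whole-cohort change it is usable on precision. For the subtype question the answer depends on a split that cannot be known beforehand, since prevalence is itself a secondary objective and no IgE cut-off is given. The claim that a subtype of 5 could never reach 0.050 (smallest exact two-sided signed-rank p = 2/32 = 0.0625) needs both that split and an exact test within the subtype, and the plan specifies neither.

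Finally, this is a small single-site cohort, and strict alpha control over secondary scores is partly a matter of preference. That is fair, but the plan does not call itself exploratory, and it declares significance at 0.050.

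**Conclusion.** The point holds in this form. The named primary outcome lacks a visit and a designated comparison; the primary objective leaves at least 11 over-time comparisons unranked; all are tested at 0.050; and 33 rests on precedent, with no precision stated for the comparison by local IgE status. With no true effect, at least one significant result is expected in about 17% of trials for the four candidate analyses of the named outcome (18.5% if independent) and in about 26-37% for the 11 (43% if independent). These rates rest on assumed correlations and, for the four, a 16/17 split; the gaps in the text do not depend on them. This should be corrected, but it does not invalidate the data collection or the target of 33.

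**What to change.** Make these changes before outcome data are examined. The Publication Plan anticipated recruitment from April 2019 and this version is dated 05/25/2022. That does not show that data have been seen; if they have, say so and label the choice post hoc.

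- **(a) One primary analysis.** Name one visit and one comparison for change in major-symptom VAS. Label total and individual VAS, the other visit and optical density as secondary, without confirmatory claims at 0.05.
- **(b) Settle the subtype question.** Either make the primary comparison the change in major-symptom VAS between patients with and without local IgE elevation, reported as an estimate with its CI, or choose whole-cohort pre/post and state openly that the subtype question becomes secondary. Align the Objectives with the choice.
- **(c) If pre/post is used,** report it as uncontrolled change, not treatment effect, and do not treat p < 0.05 against zero as evidence of efficacy. Where an enrollment score separate from the screening score exists, use it as baseline.
- **(d) Replace the sentence that sets 33** with wording such as:

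> The target of 33 completers is set by precedent. It estimates whole-cohort mean change in major-symptom VAS to within about +/-0.35 SD, and 25/33 successes with a 95% CI of about 58% to 89%. A subtype difference in change is estimated only to within about +/-0.7 SD (16/17) to +/-1.0 SD (5/28); these splits are assumptions. A non-significant subtype result is not evidence of equal response.

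**Cost.** No extra patients, visits or measurements. Fewer results can be claimed as confirmatory, and the stated justification for 33 is less favourable. If pre/post is made primary, the study's subtype question is demoted, which is a change of objective and not only of wording.

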Differences between all continuous descriptive factors and both pretreatment and posttreatment outcome measure scores, between participants with and without local IgE elevation, will be evaluated using Mann Whitney U or chi-square (χ^2) testing where appropriate. Significant improvements in outcome measure scores over time and between pretreatment and posttreatment scores will be evaluated using Wilcoxon signed rank tests. Significant differences will be identified at a conventional 0.050 alpha level.

Ethics

- IRB approval will be sought from CPHS
- Prior to obtaining consent, the study and the subject's participation requirements will be fully explained to the subject. They will be given ample time to read the consent, as well as to ask questions. If needed, a copy of the consent can be provided to take home if additional time is needed to review. Consent will then be obtained after the subject has had adequate time to assess the study.

Data handling and record keeping

- Access to source documents will be limited to study personnel with appropriate training.
- Source documents will be de-identified appropriately. Subjects will be assigned a subject number which will be associated with all data gathered from that subject.
- Subjects will be identifiable through their subject number via an excel spreadsheet which links PHI with subject number. The ability to identify subjects via their subject number will only be available to study personnel with appropriate training.
- All data stored in a password protected excel document will be saved on a UT issued password protected laptop.
- All source documents will be stored in a secured filing cabinet within the locked otolaryngology clinic located at [name].

Quality control and assurance

- Printed protocol will be available during data collection to ensure that all steps are followed consistently
- Personnel will be available to answer questions regarding questionnaire completion to ensure that all questions are answered and answered appropriately
- Source documents will be saved to confirm integrity of the data transferred to excel documents for analysis.

Publication Plan

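### The Statistics section compares local-IgE subtypes on raw scores only; it names no between-subtype comparison of change in major-symptom VAS or of the 30% response

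*Combined protocol and SAP*

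**What the plan says.** The last paragraph of the Background states the gap that the study addresses: "we do not know whether certain subtypes of idiopathic rhinitis are more likely to respond to treatment with intranasal capsaicin treatment than other subtypes". The primary objective is therapeutic response in patients subtyped by local IgE.

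The first paragraph of the Statistics section names the outcome, "we considered our primary outcome as the change in VAS for the major nasal symptom", with "success defined as a decrease of at least 30% on the VAS for the major nasal symptom".

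The second paragraph assigns the tests:

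- By IgE status: "both pretreatment and posttreatment outcome measure scores, between participants with and without local IgE elevation, will be evaluated using Mann Whitney U or chi-square" testing where appropriate. The same sentence covers continuous descriptive factors.
- Over time: "Significant improvements in outcome measure scores over time and between pretreatment and posttreatment scores will be evaluated using Wilcoxon signed rank tests". Subtype is not mentioned here.

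Two other places describe comparisons, both across time points: the primary objective ("The total as well as individual symptom VAS scores at enrollment, 4 weeks post-treatment, and 12 weeks post-treatment will be compared") and the Study Design section ("The pre- and post-treatment data can be compared to measure change in symptoms").

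**The concern.** The outcome is a change and the question is whether that change differs by subtype, but no sentence joins the two. As written, a claim about subtypes would rest on one of two things. The first is a comparison of posttreatment scores, which mixes response with baseline severity. The second is a reading of separate within-subtype signed-rank p-values side by side, which does not test a difference between subtypes. The first can show a difference when response is the same, or hide a real one. The choice of scale and time point for a direct comparison would also be open until after the data are seen.

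**Working it through.** **Plan's own figure.** The 33 completers are taken over from the size of the cited capsaicin study. No null rate, power or formula is given, so there is no calculation to reproduce, and no stated figure is contradicted here.

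**Inputs.** From the Statistics section: alpha 0.05 (two-sided assumed), N = 33, 75% response, response meaning a fall of at least 30%. The documents give no VAS SD, pre-post correlation, baseline gap or subtype split, so every such value below is an assumption. Simulations used 10,000 trials per setting.

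**What each test targets.** Let g be the baseline gap between subtypes and δ the subtype difference in mean change. The posttreatment difference is g + δ. The planned between-subtype test therefore addresses g + δ = 0, and a test on change addresses δ = 0. They ask the same question only when g = 0.

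**Equal absolute change (δ = 0), split 16/17.** For Mann-Whitney with normal scores and a shift of d SD, k = d × √(3/π × n1n2/(n1+n2)), and rejection ≈ Φ(k − 1.960) + Φ(−k − 1.960). Here √(0.955 × 16 × 17/33) = 2.806.

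- g = 0.5 SD: k = 1.403, rejection ≈ 29%.
- g = 0.8 SD: k = 2.244, rejection ≈ 61%.

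This large-sample formula runs slightly high. Simulation with correlation 0.3 to 0.7 gives 26-28% and 57-58%, against 4-5% for a test on change. At 8/25 the posttreatment figures are 20% and 43-44%; at 3/30 they are 10-11% and 21-22%.

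**A hidden difference.** If a true 0.8 SD difference in change is offset by a 0.8 SD baseline gap, g + δ = 0. The posttreatment test then rejects in about 5% of trials and a test on change in 44-79%.

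**Dependence on what equal response means.** VAS 0-10, baseline mean 6, SD 1.5, gap 1.5 points (1 SD), split 16/17; rejection when response is equal:

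| Equal response means | Posttreatment | Absolute change | Percent change |
|---|---|---|---|
| Same fall in points (3) | 47% | 5-6% | 21% |
| Same proportional fall (50%) | 22% | 22% | 5% |
| Same expected posttreatment score at the same baseline, correlation 0.3 | 13% | 36-38% | 4-11% over the settings tried |

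The third row can be checked by hand. With correlation ρ, the posttreatment shift is ρg = 0.3 SD, so k = 0.842 and rejection ≈ 13%. The change shift is (1 − ρ)g/√(2(1 − ρ)) = 0.7/√1.4 = 0.592, so k = 1.660 and rejection ≈ 38%. A baseline-adjusted model stays at 5-6% in that row. It is not immune either: under equal absolute change its expected difference is (1 − ρ)g, for example 0.7 × 0.8 = 0.56 SD. In the first two rows' models, a Fisher test on the 30% response stays at 3-6%.

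**Power of the direct comparison.** Proportional model, 75% responders against 55/45/35%, split 16/17, no gap:

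- percent change: 31/58/81%
- posttreatment: 24/44/65%
- responders (Fisher): 15/35/60%

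For 75% against 45%, if the better-responding subtype starts 0.75 or 1.5 points higher, posttreatment power falls to about 19-20% and 7%, while percent change stays at 57-59%. With uneven splits, percent-change power is 23/43-44/67% at 8/25 and 12-13/22/34% at 3/30. With an SD of 25 percentage points, the 95% CI half-width is about 19, 22 and 35 points at 16/17, 8/25 and 3/30. With one patient in a subtype, the smallest exact two-sided p is 2/33 = 0.061.

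**The case against.** **The chi-square clause.** The plan's wording, "will be evaluated using Mann Whitney U or chi-square (χ^2) testing where appropriate", may already cover responders. Response is the only binary outcome defined, and the descriptors in that sentence are limited to continuous ones, so this reading fits at least as well as any other. It stands as a possibility. But the sentence lists descriptive factors and scores and never mentions response, and the clause would not supply a comparison of change.

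**A within-subtype aim.** The General Information section asks about response in patients with local IgE elevation, the primary objective can be read as response within each subtype, and the sample size rests on a single 75% rate. Signed-rank tests run by subtype would serve that aim, although the plan does not say they will be run that way. This softens the point. It does not remove it, because the Background question and the plan's own comparison by IgE status call for a contrast.

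**Conditional harm.** The plan also compares pretreatment scores, so it looks for the gap on which the harm depends. That is true, but a non-significant baseline test in 33 patients would not exclude a gap, and finding one would not correct for it. It is also fair that the 27-58% figures follow from defining equal response as equal absolute change. Under the third definition in the table, raw posttreatment scores do better than unadjusted absolute change when correlation is low.

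**What a reader might infer too far.** One might conclude that the plan has no between-subtype test, or that its test has a false-positive rate of 27-58%. Neither is supported. With equal baselines the posttreatment comparison is a valid indirect test, and nothing in the documents says that baselines differ.

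**Conclusion.** The concern holds as a gap in specification: the contrast that the Background asks for is not named on the outcome that the Statistics section defines, and the contrast that is named answers it only if baselines are similar. Confidence is high on the text. The size of the effect is conditional on a baseline gap that no document reports, on the assumed SD, correlation and split, and on how equal response is defined. For a gap of 1.5 points, posttreatment rejection with equal response ranges from 13% to 47% across the three definitions tabulated. The point should be fixed before analysis. It does not invalidate the study, and it does not show that the posttreatment comparison would mislead here.

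**What to change.** In the second paragraph of the Statistics section:

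1. Name one two-sided Mann-Whitney comparison, between participants with and without local IgE elevation, of percent change in major-symptom VAS from enrollment to week 12, with an estimate and 95% CI. Percent change matches the 30% success definition.
2. As sensitivity analysis, add a baseline-adjusted comparison of week-12 VAS, in place of or alongside unadjusted absolute change.
3. Report the 30% responder rate by subtype (Fisher exact, difference and 95% CI) as supportive, and say what the chi-square wording was meant for.
4. Keep the raw pretreatment and posttreatment comparisons as descriptive, and state that no subtype difference will be inferred from separate within-subtype p-values.

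Percent change and week 12 are choices that the documents do not force; what matters is that scale and time point are fixed before data are seen.

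The cost is a few sentences, since the enrollment and week-12 scores are already collected. No scale is immune to a baseline gap: percent change rejects in up to about 21% of trials if response is a fixed number of points, and unadjusted absolute change in up to about 38% at low correlation. Power is limited at 33 patients and lowest for the responder comparison. The Background cites a series in which 20 of 20 such patients had antigen-specific IgE. A split that uneven could leave any subtype comparison uninformative, and this change does not solve that.
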